Small amount of blood [3 lavender topped tubes] will be collected from subject to test for hemoglobin, type & screen and 1 cross match to verify the donated blood received from

RESEARCH Summary

Pro00078468

NCT03089047

PI: [name]

The Blood Connection belongs to the same subject who arrives at the appointed date at Duke facility

Anemic VO₂max

Three minutes of resting baseline measures will be recorded before the start of exercise. The subject will then begin to pedal the cycle ergometer at a cadence of 75 rpm. Resistance will be manually set according to a standardized, progressive protocol. A rating of perceived exertion (RPE) will be obtained at the end of each exercise stage. Vital signs will be recorded every 3 minutes, and ECG monitoring will be continuous. Exercise will be terminated when the subject reaches volitional fatigue. VO₂max will be reported as the highest oxygen consumption averaged over two 30-second periods, which typically occurs in the last stage of the progressive maximal exercise test. Maximum heart rate will be the heart rate at or near VO₂max. To minimize variability in VO₂max testing procedures, the same 2 facilitators (an engineer/technician and a research staff) will be present at every test. Radial arterial access will be obtained for cardiac output monitoring (LiDCO pulse contour analysis) at this visit.

Tx and post-Tx VO₂max

Duke Transfusion Services will randomize each subject to receive 2 units of standard PRBCs or rejRBCs over 120 minutes using a standard infusion pump. All units will be washed to equalize the transfusion volumes; rejuvenation includes a mandatory washing step. Rejuvenation of donated blood will be done according to the procedures in the labeling of the Rejuvesol product. Vital signs will be monitored and recorded every 15 minutes. After a total 4-hour rest after completing the first VO₂max testing, and a light snack, the exercise test will be repeated.

Laboratory testing: The p50 will be measured in one of the blood units transfused and in the subject before the exercise test. Radial arterial access will be obtained for serial cardiac output monitoring (LiDCO Pulse Contour Analysis, LiDCO Products, London, UK), arterial blood gas analysis and lactate measurement before and after transfusion, and after exercise testing. Final blood collected for a hemoglobin level will be done at the conclusion of blood transfusion. This is the final visit and participation is completed.

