VO₂ max is determined as the highest oxygen consumption averaged over two 30-second periods, which typically occurs in the last stage of the progressive maximal exercise test. Peak heart rate is considered to be heart rate at VO₂ max. Maximum heart rate (HR_{max}) is considered to be heart rate at or near VO₂ max.

Termination Criteria for VO₂ max Test

1. Subject fatigue or subject request for any reason
2. Inability to maintain the prescribed cadence (75-80 rpm) at the current work rate
3. Onset of chest pain or equivalent angina symptoms, such as unusual or extreme shortness of breath, or signs of poor perfusion, as noted by the subject or determined by the monitoring physician
4. Sequential ventricular beats of two or more (ie, 2 beats of ventricular tachycardia)

Stage	Time (min)	RPM (rpm)	Total Workload (watts)	Leg Load (kp)
1	0 - 3	75	50	0.68
2	3 - 6	75	100	1.36
3	6 - 9	75	150	2.04
4	9 - 10	75	175	2.38
5	10 - 11	75	200	2.72
6	11 - 12	75	225	3.06
7	12 - 13	75	250	3.4
8	13 - 14	75	275	3.74
9	14 - 15	75	300	4.08
10	15 - 16	75	325	4.42
11	16 - 17	75	350	4.76
12	17 - 18	75	375	5.1
13	18 - 19	75	400	5.44
14	19 - 20	75	425	5.78
15	20 - 21	75	450	6.12

RESEARCH Summary

Pro00078468

NCT03089047

PI: [name]

5. New onset of sustained (>15 seconds) atrial fibrillation, supraventricular tachycardia (SVT), or other supraventricular tachyarrhythmias
6. Development of new left bundle branch block (LBBB)
7. Systolic blood pressure >240 mm Hg, or diastolic blood pressure >130 mm Hg
8. Progressive decrease in heart rate or systolic blood pressure during increasing exercise intensity accompanied by clinically significant signs or symptoms
9. Second-degree Type II or third-degree heart block.

To minimize variability in VO₂ max testing procedures, whenever possible, the same 2 facilitators will be present at every test ([name] - engineer/technician for VO₂ max equipment; a nurse Research Coordinator who will collect data and coach each subject).

Additional Measurements During VO₂ max Testing

On the Day 14 visit for VO₂ max testing, the following additional study procedures will be performed:

- A radial arterial catheter will be inserted under local anesthetic prior to exercise testing, consistent with previous studies on healthy volunteers done in our laboratory.

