- Arterial blood samples (6 mL each) will be obtained from the radial arterial catheter immediately before exercise, twice during exercise, and after exercise completion (total 24 mL). Blood samples will be analyzed for arterial lactate, PO₂, PCO₂, and pH. We know that arterial lactate increases during VO₂ max testing, and we will conduct exploratory analyses to determine whether there are differences in peak lactate between study arms (Standard vs Rejuvenated RBCs).
- Cardiac output, cardiac index, and stroke volume will be determined during VO₂ max testing using the validated and FDA-approved LiDCO monitor, which includes a lithium dilution determination of cardiac output, with subsequent measurements from radial arterial pulse contour analysis. These data will be used to confirm that cardiac output is similar for subjects in the two study arms, ie, no difference in VO₂ max is attributable to differences in cardiac output between study arms. We do not expect to see any differences in cardiac output between groups since the study arms will receive an identical volume of fluid (2 RBC units) over the 2-hour transfusion period.

Detailed Description of Rejuvenation Process: Rejuvenation refers to the process of adding a mix of solutes (Rejuvesol®, Citra Labs, Braintree, MA; consists of sodium pyruvate, inosine, adenine, mono- and dibasic sodium phosphate) to older, stored (i.e., 2-3 DPG-depleted) blood to immediately restore 2,3-DPG and ATP levels in the stored red blood cells¹⁵. Rejuvenation was originally developed to prolong the storage life of rare-phenotype RBC units. It is FDA-approved for use in RBC units stored in CPD, CPDA-1, and AS-1. The major contraindication for the use of Rejuvesol® is in RBC units stored for fewer than 6 days due to high baseline 2,3-DPG and ATP levels.¹⁶ Rejuvenated blood should not be used in patients with PaO₂ < 40 mmHg due to the impaired pulmonary oxygen loading at low arterial oxygen tensions seen with high-p50 hemoglobin; we will appropriately exclude these patients at the first screening visit.

RESEARCH Summary

Pro00078468

NCT03089047

PI: [name]

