9. Data Analysis & Statistical Considerations: The primary outcomes of this study are the change in $VO_{2\max}$ and lactate between the “anemic” $VO_{2\max}$ and after transfusion of 2 units of either standard PRBCs or rej-PRBCs “post-Tx” $VO_{2\max}$. We hypothesize that transfusion of RBCs is less effective at increasing oxygen delivery (measured by $VO_{2\max}$ and lactate) compared with transfusion of rej-PRBCs. We expect the changes to be normally distributed and will compare the treatment groups with a 2-group t-test or a rank-sum test if the distribution is non-normal. We will test at a 2-sided significance level of 0.05. The primary analysis will be on an intent-to-treat basis, with follow-up as-treated analysis if necessary. Subjects who withdraw or are excluded before randomization (Day 14) will simply be dropped from analysis. We will further examine the treatment effect in a multivariable regression adjusting for potential effects of baseline $VO_{2\max}$, lactate, hemoglobin, and BMI.

Secondary outcomes include the change in “post-Tx” $VO_{2\max}$ from baseline and differences in these changes will be compared between groups with t-tests or rank-sum tests. Of note, in contrast to the primary endpoint, this secondary analysis may show larger increases in $VO_{2\max}$ attributable to hypervolemia after transfusion. Duration of exercise and peak lactate “post-Tx” will also be compared between study groups.

Based on preliminary data ([name], personal communication), we know that 2 units of autologous, stored PRBCs increase $VO_{2\max}$ on the day of transfusion by $2.4 \pm 0.6 \text{ ml/kg/min}$. Assuming that rej-PRBCs exceed the oxygen delivery of native fresh blood (due to their $p50$ of 40 mmHg compared to 18 mmHg for stored PRBCs and 28 mmHg for normal blood), we anticipate that:

- Pre-transfusion/“anemic” $VO_{2\max}$ will be decreased by 4.6 ml/kg/min from baseline by day 14.
- 2 units rej-RBC will increase $VO_{2\max}$ by $> 6 \text{ ml/kg/min}$ from “anemic” $VO_{2\max}$.
- 2 units control PRBC will only increase $VO_{2\max}$ by 2.5 ml/kg/min from “anemic” $VO_{2\max}$.
- Therefore we will set our expected, measured difference (δ) at 3.5 ml/kg/min .

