Preliminary data also show that the variability of $VO_{2\max}$ has a narrow range, with standard deviation ranging from $0.8-1.9$ for a given subject ([name], personal communication). Combining with our preliminary data (which showed an increase after transfusion of $2.4 \pm 0.6 \text{ ml/kg/min}$ – see above), we set our standard deviation for the power analysis (σ) at $\pm 1.5 \text{ mL/kg/min}$.

Using this data, we can expect 80% power to detect a significant ($p < 0.05$) intergroup difference in the change in $VO_{2\max}$ from anemic to post-transfusion state with 3 volunteers in each group. More patients will be studied as unexpected variability may occur.

10. Data & Safety Monitoring: We will record and analyze both expected and unexpected adverse events in order to monitor for and minimize potential risks to

RESEARCH Summary

Pro00078468

NCT03089047

PI: [name]

human subjects. Adverse events that occur during any study procedure will be collected and reported to the IRB, and FDA as appropriate. The Principal Investigator will review serious and non-serious AEs on a rolling basis as well as in aggregate on a monthly basis. Given the long standing safety of VO₂ max testing as well as blood collection and transfusion studies (many removing far larger volumes of RBCs) we do not expect to see a significant number of adverse events.

11. Privacy, Data Storage & Confidentiality: Study records that identify the patient will be kept confidential as required by law. They will be kept in a locked file cabinet in either the Study Coordinator's or [name] office. Data will also be stored in password protected computers. Except when required by law, the subject will not be identified by name, social security number, address, telephone number, or any other direct personal identifier in study records disclosed outside of Duke University Health System (DUHS). The results of this research study may also be presented at meetings or in publications; however, identity will never be disclosed in those presentations. In no way will any subjects' name be used in any published form.

As part of the study, [name] and the study team will report the results of the study-related laboratory tests named below. These test results will be recorded in the study record and results of tests and studies done solely for this research study will not be included in the volunteer's medical record.

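### Changes in VO₂max and lactate are both primary at one 0.05 level with no rule linking them, and the lactate sample that defines the change is not named

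*Combined protocol and SAP*

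**What the plan says.** **Outcomes and level.** Section 9 (Data Analysis & Statistical Considerations) begins "The primary outcomes of this study are the change in $VO_{2\max}$ and lactate between the" anemic and post-transfusion tests. Its hypothesis sentence again gives both measures. The level appears once: "We will test at a 2-sided significance level of 0.05". No section gives a success rule, a testing order or an alpha split.

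**Signs that VO₂max leads.** The Purpose (Section 2) and the closing hypothesis of the Background (Section 3) measure oxygen delivery by VO₂max alone. Section 9 introduces a secondary analysis with the words "in contrast to the primary endpoint, this secondary analysis may show larger increases", where the endpoint is singular and concerns VO₂max. The sizing says "we can expect 80% power to detect a significant" difference in the VO₂max change "with 3 volunteers in each group". No lactate effect or SD is given anywhere.

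**Lactate sampling.** Section 5 (Additional Measurements During VO₂ max Testing) says that on the Day 14 visit "the following additional study procedures will be performed". These include arterial samples "immediately before exercise, twice during exercise, and after exercise completion (total 24 mL"). Section 4 (Laboratory testing) describes "lactate measurement before and after transfusion, and after exercise testing". Peak lactate is named only as an exploratory comparison in Section 5 and among the secondary comparisons in Section 9.

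**The concern.** With two primary outcomes at one level and no rule linking them, the plan does not say which pattern of results supports the hypothesis. Suppose VO₂max is not significant and lactate is. One reader would call the trial negative, and another would say a primary outcome was met. Both can point to Section 9.

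The lactate outcome is also incompletely defined. Section 9 fixes the two occasions, the anemic and post-transfusion tests, but not the sample within each. The primary lactate contrast could therefore be settled after the data are seen.

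**Working it through.** **Inputs from the documents.** Two-sided alpha 0.05, two-group t-test, δ = 3.5 and σ = 1.5 mL/kg/min for the VO₂max change, and 3 per group (all Section 9). Section 4 gives 10 donors in one place and 20 enrolled in another.

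**Assumptions.** 1:1 allocation, hence 5 or 10 per arm; the success rule; the correlation between outcomes; and any lactate effect. None of these is stated in the documents.

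**1. The plan's own figure.** By the normal formula, n = 2 × [1.5 × (1.960 + 0.842) / 3.5]² = 2.88, rounded up to 3 per group, with power 81.5%. The stated size reproduces, and it uses VO₂max inputs only. The planned t-test gives 58.0% power with 3 per group; that shortfall is a separate matter.

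**2. Either outcome counts.** For independent tests, familywise error = 1 − (1 − 0.05)² = 0.0975. The bound at any correlation is 0.05 + 0.05 = 0.10. Simulated pairs of two-sided t-tests with no effect on either outcome give:

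| Per arm | Correlation 0 | 0.5 | 0.9 |
|---|---|---|---|
| 5 | 9.7% | 9.2% | 7.3% |
| 10 | 9.8% | 9.2% | 7.1% |

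The result hardly depends on which planned size is right.

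**3. Both outcomes required.** With no effect on either, both tests reject in 0.25%, 0.8% and 2.7% of trials at correlations 0, 0.5 and 0.9 (5 per arm). If only one outcome has no effect, the error is at most 5%. There is no inflation.

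Power is a different matter. VO₂max alone at 5 per arm (noncentral t, d = 3.5/1.5 = 2.33) has 89.6%. Joint power also needs a lactate effect and SD, which the plan does not give. As one illustration, an assumed lactate effect of 1 SD has 28.6% power alone at 5 per arm (noncentrality 1 × √(5/2) = 1.58, 8 degrees of freedom). At correlation 0, joint power is 0.896 × 0.286 = 0.26. By simulation it runs from about 22% at correlation −0.9 to 29% at 0.9.

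**4. Which lactate change.** Section 5 lists four sampling points: one before, two during and one after exercise. At 6 mL each, 4 × 6 = 24 mL, the stated total. That is one set, whereas Day 14 contains two exercise tests. Section 4 ties sampling to transfusion and to the end of exercise testing instead. If the four-sample set is drawn in both tests, several like-for-like changes could serve as the primary result. If it is drawn once, fewer could.

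**5. VO₂max first, lactate gated.** Lactate is tested only after VO₂max rejects at 0.05, so familywise error over the two comparisons is at most 0.05. VO₂max keeps its full level and its 89.6% power at 5 per arm.

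**The case against.** The strongest reply is that this is a pilot, described in the Background as a proof-of-principle step, and that no confirmatory claim rests on it. Section 9 sets a level for testing and does not promise familywise control. VO₂max is the lead outcome everywhere except the sentences in Section 9 that add lactate, and the hypothesis there joins the two measures with *and*, which can be read as requiring both. Peak is the only lactate summary the plan names, and because lactate rises with exercise, a resting sample is an unlikely choice.

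Much of this stands, and it limits the point. A reader might infer that the trial's type I error is nearly 10%. The documents do not support that, because the figure needs an either-counts rule that no section states. A reader might also infer that four rival lactate changes are certainly available. That depends on the full set being drawn in both Day 14 tests, and the 24 mL total covers one set. Nor can joint power be called low as a fact about this trial, since it rests on an assumed lactate effect.

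The reply does not remove the gap. The defining sentence names two primary outcomes, and nothing ranks or links them. Peak lactate is listed as secondary or exploratory, so it cannot simply be taken as the primary definition. The pilot label does not say which result answers the hypothesis.

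**Conclusion.** The omission is real and cheap to repair. Section 9 makes two outcomes primary at one 0.05 level without a success rule, order or split, although the rest of the plan points to VO₂max.

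The size of the problem is conditional:
- **Either counts:** familywise error is about 7% to 10% over correlations 0.9 to 0, assuming t-tests and 1:1 allocation.
- **Both required:** there is no inflation, but the stated power does not describe the chance of success, and that chance cannot be computed from the documents.

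Separately, the primary lactate change is not tied to a sample. In a pilot, the practical consequence of both gaps is limited to how a lone significant lactate result may be reported.

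**What to change.** In Section 9, state that the anemic-to-post-transfusion change in VO₂max is the primary outcome, tested at two-sided 0.05. Test the lactate change at 0.05 only if VO₂max is significant, and otherwise report it descriptively. Fix the test for each outcome in advance.

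Define the lactate change by one already planned sample taken in both Day 14 tests. The post-exercise sample is an example, since Sections 4 and 5 both list it. As minor wording, give peak lactate one label in Sections 5 and 9, and say whether the 24 mL total is per test.

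**Cost.** Lactate loses equal primary status. VO₂max power is unchanged, and no new subjects are needed. No new procedures are needed either, provided the sampling is already meant for both tests. If the sponsor prefers equal status, 0.025 for each outcome also holds the error (1 − 0.975² = 0.0494 if independent, at most 0.05), but VO₂max power at 5 per arm falls from 89.6% to 80.2%.

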2) The Blood Connection (TBC) is located in Piedmont, SC with a satellite in Raleigh, NC and was established in 1962. The Blood Connection is registered and licensed by the US FDA and accredited by the American Association of Blood Banks. TBC has two blood mobiles, which travel throughout the Triangle and one fixed site where blood is collected and products are produced. Blood collection is performed by single whole blood donation and automated apheresis for the collection of red cell, plasma and platelets. TBC (Raleigh) processes approximately 18,000 donations per year, manufactures red blood cell products, frozen plasma products, and platelet products; in North Carolina TBC is the primary supplier to Wake Med and Rex Hospitals in Raleigh. They also supply Duke University Medical Center, as inventory and need allows, especially for autologous units. The VP Business Development/Chief Technical Officer of TBC ([name]) and the medical director ([name]) has agreed to allow the blood collections and processing for this study to take place at TBC using their standard procedures for autologous blood collection by apheresis. A fee is being charged to Duke for these services as if this were a standard autologous donation.

Study size:

In this pilot study, we will plan to enroll 20 subjects.

Eligibility Criteria:

Healthy, habitually exercising, non-smoking, non-diabetic males and females (as described in the inclusion/exclusion criteria below):

Qualified volunteers will be enrolled at a single center (Duke University Medical Center). After subjects provide written informed consent, eligibility will be confirmed with a questionnaire and screening tests (below). We have used these methods before, and they are designed, in large part, to insure the safety of participants.

Inclusion Criteria:

- i. Healthy male or female
- ii. Age 18-40 (the American College of Sports Medicine Guidelines for Exercise Testing defines this age group with no or no more than one coronary heart disease risk factor as low-risk for VO₂ max testing)
- iii. Habitual exerciser defined as ≥ 30 minutes of at least moderate or high intensity exercise ≥ 3 times per week. After consent, and at the subsequent screening visit, a VO₂ max test will be performed, and subjects with a low value (< 30 mL/kg/min) will be excluded (screen failure). Based on our

RESEARCH Summary

Pro00078468

NCT03089047

PI: [name]

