previous experience, we anticipate that up to 25% of the subjects will fall into this category; therefore, 20 subjects will be screened to obtain 10 participants who go on to donate their blood.

- iv. Calculated total blood volume of at least 4,500 mL using an established formula:

- a. Men: $(0.006012 \times H^3) + (14.6 \times W) + 604 = TBV$
- b. Women: $(0.005835 \times H^3) + (15 \times W) + 183 = TBV$

[H= Height in inches; W=Weight in pounds]

- v. Has access to transportation to visit the blood collection facility and to return to Duke for all study visits
- vi. Weighs at least 130 pounds

Exclusion Criteria:

- i. Any significant acute or chronic medical illness or problem, including, but not limited to, diabetes, hypertension, cardiac disease, asthma, COPD
- ii. Current or recent (last 60 days) tobacco or nicotine use
- iii. History of sickle cell trait or disease or any other acquired or hereditary hematological abnormality
- iv. History of fainting or other significant adverse reaction during phlebotomy or donation of blood
- v. Known prolonged QTc (or evidence of such at screening) defined as QTc >470 ms
- vi. Known or suspected illicit drug or alcohol abuse
- vii. Known or suspected HIV, Hepatitis B, or Hepatitis C infection
- viii. History of thrombophilia or anticoagulant therapy
- ix. Pregnancy
- x. Obesity defined as BMI>30
- xi. Recent history of blood donation:
 - a. Single whole blood unit donation within the past 8 weeks
 - b. Double RBC donation by apheresis within the past 16 weeks
 - c. Plasma donation by apheresis within the past 4 weeks
 - d. Any self-reported blood donation within a year
- xii. Inadequate red blood cell mass evidenced by total blood volume <4500 mL (above) or screening hemoglobin <13.3 g/dL
- xiii. Known hypersensitivity to lithium compounds. And known taking lithium salts for treatment of other medical/psychiatric conditions

RESEARCH Summary

Pro00078468

NCT03089047

PI: [name]

xiv. Students and employees who are under direct supervision of the investigators

Study structure: study visits (A-E).

A	Screen	Screen, consent, H&P, ECG, screening labs, and VO ₂ max
B	Day 0	Donate 2 units of PRBCs by autologous apheresis
C	Day 14	8am Measure pre-transfusion, “anemic” VO ₂ max 9 am Transfuse 2 units of standard or rejuvenated PRBCs 3 pm Measure post-transfusion VO ₂ max (end of study)

listed in this study.

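### Exercise duration, a secondary endpoint, is compared between arms with no stated use of each subject's own same-day anemic duration

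*Combined protocol and SAP*

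**What the plan says.** Section 9 (Data Analysis & Statistical Considerations) builds most of its comparisons on within-subject change. It opens with "The primary outcomes of this study are the change in" VO₂max and lactate, from the anemic test to the post-transfusion test. The hypothesis likewise measures oxygen delivery by VO₂max "and lactate) compared with transfusion of rej-PRBCs". The arms are compared by a "2-group t-test or a rank-sum test if the distribution is non-normal", and "We will test at a 2-sided significance level of 0.05". The same paragraph adds a regression: "We will further examine the treatment effect in a multivariable regression adjusting for potential effects of baseline" VO₂max, lactate, hemoglobin and BMI.

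The next paragraph covers secondary outcomes. The VO₂max secondary outcome is again a change, this time from baseline. The remaining two are described differently: "Duration of exercise and peak lactate “post-Tx” will also be compared between study groups". No pre-transfusion value enters that sentence.

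The Study structure table in Section 4 has each subject, at 8 am on Day 14, "Measure pre-transfusion, “anemic” VO ₂ max"; the post-transfusion test follows at 3 pm. The Visit C text describes the second as a repeat of the first. Inclusion criterion iii sets a lower limit on fitness: "subjects with a low value (< 30 mL/kg/min) will be excluded". No upper limit is given.

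**The concern.** An anemic exercise duration exists for every subject who reaches the second test, and no analysis is stated to use it. The regression sits in the primary-outcome paragraph, is not clearly extended to secondary endpoints, and does not list anemic duration.

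Duration is more exposed than VO₂max per kilogram. The stage table in Section 5 fixes the load in watts, from 50 to 450 W over 21 minutes, the same for everyone. Entry admits both sexes, ages 18-40, weights from 130 lb and any VO₂max of at least 30 mL/kg/min. How long a subject lasts therefore depends in part on how fit and how large that subject is, whatever was transfused. In a trial this small, an uneven split of those traits could hide a treatment effect on duration or look like one. Duration would then give weak support, or none, to the VO₂max result.

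**Working it through.** **Inputs from the documents.** Expected difference in VO₂max change 3.5 mL/kg/min; SD for power 1.5; single-subject SD 0.8-1.9; 80% power with 3 per group; two-sided 0.05 (all Section 9). Ten donors from 20 screened (Section 4, inclusion criterion iii).

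**Assumptions.** 1:1 allocation, so 5 per arm. Between-subject SD of VO₂max from 1 to 8 mL/kg/min; the documents give none. They also give no SD, effect or correlation for duration, so steps 2 and 3 use VO₂max as a stand-in.

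**1. The plan's own figure.** n = 2(1.5/3.5)²(1.960 + 0.842)² = 2.88, rounded up to 3 per group. Normal-approximation power at n = 3 is 81.5%, so the stated 80% reproduces. The exact noncentral t gives 58.0%. Both concern VO₂max change; no power is stated for duration.

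**2. Level against change, 5 per arm.** Noncentrality = 3.5/(SD × √(2/5)), 8 degrees of freedom. SD of change = s_w√2 and SD of level = √(s_b² + s_w²), where s_w is the single-test SD and s_b the between-subject SD. The plan's change SD of 1.5 implies s_w = 1.5/√2 = 1.06. At the top of the quoted range, s_w = 1.9 and the change SD is 1.9 × √2 = 2.69.

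| Comparison | s_w = 1.06 | s_w = 1.9 |
|---|---|---|
| Change | 90% | 44% |
| Level, s_b = 1 | 91% | 62% |
| Level, s_b = 2 | 57% | 42% |
| Level, s_b = 4 | 22% | 20% |
| Level, s_b = 6 | 13% | 12% |
| Level, s_b = 8 | 9% | 9% |

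Worked cell: s_b = 4, s_w = 1.06 gives level SD 4.14 and noncentrality 3.5/(4.14 × 0.632) = 1.34, hence 22%. With 10 per arm and s_w = 1.06, level power is 90%, 43%, 23% and 15% at s_b = 2, 4, 6 and 8.

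**3. Chance imbalance.** The SD of the difference in arm means of fitness is s_b√(2/5): 1.3, 2.5, 3.8 and 5.1 mL/kg/min for s_b = 2, 4, 6 and 8, against an expected effect of 3.5.

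**4. In minutes.** From stage 4 the load rises 25 W per minute. Assuming 10-11 mL O₂/min per watt and body weight 60-90 kg, 3.5 mL/kg/min corresponds to 3.5 × 60/11/25 = 0.8 up to 3.5 × 90/10/25 = 1.3 minutes.

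**5. Which use of the anemic value.** With within-subject correlation ρ, SD(change) = SD(level) × √(2(1−ρ)) and SD(adjusted) = SD(level) × √(1−ρ²). For an assumed effect of 1 level SD and 5 per arm:

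| ρ | Level | Change | Adjusted, 8 df | Adjusted, 7 df, variance × (1 + 1/6) |
|---|---|---|---|---|
| 0.3 | 29% | 22% | 31% | 26% |
| 0.5 | 29% | 29% | 36% | 31% |
| 0.8 | 29% | 59% | 64% | 56% |
| 0.9 | 29% | 87% | 89% | 82% |

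The last column approximates the cost of estimating one slope from 10 subjects: one degree of freedom, and an average variance inflation of 1 + 1/(10 − 4) for covariate imbalance. A raw change score beats the level only when ρ exceeds 0.5. Adjustment stays within about 5 points of the better of the two throughout.

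**The case against.** The strongest reply is that the comparison is valid as it stands. Subjects are randomized, so a post-transfusion comparison is unbiased, and these are unpowered secondary endpoints of a pilot. That is right, and it limits the point to precision and chance imbalance.

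A reader might infer that fitness differences swamp the treatment effect. The documents do not show this. The loss turns on an assumed between-subject SD: at SD 1 the level comparison does as well as change. The age band, the habitual-exercise requirement and the BMI limit all narrow the spread. The figures are also for VO₂max, which the plan already analyses as a change. What remains is that, with single-test SDs of 0.8-1.9, break-even needs a between-subject SD no larger than that. This seems narrow for the entry criteria, but carrying it over to duration is an inference.

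A reader might also infer that lactate is compared only as a post-transfusion level. The text contradicts this: change in lactate is a primary outcome, and the regression adjusts for baseline lactate. Section 5 calls the between-arm look at peak lactate exploratory. It lists four 6 mL samples totalling 24 mL, which covers one test, so a matching anemic peak is not assured.

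Finally, the post-Tx qualifier may attach to peak lactate alone. The form of the duration comparison is then unspecified, and the same sentence is still needed.

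**Conclusion.** The point holds for exercise duration. The plan states no use of the same-day anemic duration, and that value will exist. The cost is lost precision and exposure to chance imbalance; there is no bias. Its size cannot be derived from the documents. On the VO₂max scale with 5 per arm, the loss runs from none at a between-subject SD of 1 to a fall from 90% to 9% power at SD 8, with the plan's change SD. If the single-test SD is 1.9, change itself has only 44%, and the level 42% at SD 2 and 20% at SD 4. These figures assume 1:1 allocation of 10 donors and that duration behaves like VO₂max.

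For lactate the point reduces to consistency: the plan does not say which sample defines the primary lactate outcome, or how the post-transfusion peak relates to it.

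**What to change.** In Section 9, state that post-transfusion exercise duration will be compared between arms adjusted for the same-day anemic duration. Adjustment is preferred to a raw change score because the correlation is unknown and a change score loses to the level below 0.5.

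For lactate, say which sample defines the primary outcome and confirm whether lactate is sampled at both Day 14 tests. If it is, adjust the post-transfusion peak for the anemic peak; if not, label that comparison as supplementary to the primary lactate change.

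For duration the cost is one sentence, with no added procedure or data. For lactate it is a clarification, and the adjustment depends on samples that the documents do not clearly show.
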